9.10. Other Aspects

Not applicable.

10. PROTECTION OF HUMAN PARTICIPANTS

10.1. Patient Information

All parties will comply with all applicable laws, including laws regarding the implementation of organisational and technical measures to ensure protection of patient personal data. Such measures will include omitting patient names or other directly identifiable data in any reports, publications, or other disclosures, except where required by applicable laws. Alongside this, ARW will conduct the study in line with General Data Protection Regulation (GDPR), Health Insurance Portability and Accountability Act of 1996 (HIPAA) and Health Information Technology for Economic and Clinical Health Act (HITECH) regulations.

The personal data will be stored at the study site in encrypted electronic and paper form and will be password protected or secured in a locked room to ensure that only authorised study staff have access. The study site will implement appropriate technical and organizational measures to ensure that the personal data can be recovered in the event of disaster. In the event of a potential personal data breach, the study site shall be responsible for determining whether a personal data breach has in fact occurred and, if so, providing breach notifications as required by law.

To protect the rights and freedoms of natural persons with regard to the processing of personal data, at no point will patient names be captured and stored within the study database. Instead, in Austria and Germany, each patient will be assigned a single, specific, numerical code, based on a numbering system defined by Pfizer. All other identifiable data transferred to Pfizer or other authorized parties will be identified by this single, patient-specific code. The investigator site will maintain a confidential list of patients who participated in the study, linking each patient's numerical code to his or her actual identity. Investigators will be required to destroy this linkage document at the point of site close-out. In order to comply with local regulations in Germany, which states that pseudoanonymised data cannot be processed without patients' informed consent, all data captured in Germany will be completely anonymised, with no unique identifier assigned to patients, and no linkage document stored by the site in Germany. In case of data transfer, Pfizer will maintain high standards of confidentiality and protection of patients' personal data consistent with the clinical study agreement and applicable privacy laws.

In case of data transfer, Pfizer will maintain high standards of confidentiality and protection of patients' personal data consistent with the Adelphi-Pfizer Master Services Agreement and applicable privacy laws.

10.2. Patient Consent

Following IRB review in Belgium, an informed consent document must be signed by the patient (or patient's legal representative) to process pseudonymized data in Belgium. Patients (or a patient's legal representative) will be asked to sign the informed consent document through their/patient's physician. The informed consent document, version 3.0, 07 June 2023, was approved by the UZ Leuven ethics committee.

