Each data source is likely to capture a large proportion of GO-treated patients in that country, hence their selection. The Austrian, Belgian and German centres have been selected as they meet the feasibility requirements (capture the relevant data variables) and due to the sample size of GO patients that they contain. The Austrian Myeloid Registry recruits data on patients with myeloid diseases from 15 Austrian centres (excluding the Medical University of Vienna) with an estimated enrollment of 3000 patients. The eligibility criteria below are largely based upon the recommend use of GO; ensuring that the overall patient sample gathered will be clinically representative of the GO treated population.

The initiation date of 1L treatment within the indexing period will be defined as the index date. De novo AML diagnosis will be captured within the screening questions of the eCRF and fully defined for each data source within the Statistical Analysis Plan (SAP). Baseline patient demographics and clinical characteristics will be evaluated at index. Treatment patterns and effectiveness outcomes will be described throughout the follow-up period. Patients will have a minimum follow-up of 3 months defined as patients with 3 months of data, following the 1L treatment initiation. This will allow for assessment of treatment patterns and early effectiveness outcomes. Follow-up will end with the following endpoints: death, loss of data (eg, transfer to a new hospital) or end of the study period. In order to maximise the follow-up data captured necessary to accurately assess survival outcomes (EFS, RFS and OS), follow-up will extend up until either the last data available for the patient (in Austrian, Belgium, and German sites), or the date of database extraction (in the Austrian Myeloid Registry). Patients who have limited follow-up data which is not sufficient for the assessment of OS and accurate EFS and RFS, will be right-censored for the purpose of survival outcome specific analysis. Patients who die within the 3-month follow-up period would be considered eligible for inclusion in order to evaluate EFS, RFS and OS outcomes.

Figure 1. Study Schematic

Study Schematic–eCRF and secondary data dataset design

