The Austrian Myeloid Registry aims to assess the treatment patterns, clinical outcomes and quality of life of patients with myeloid diseases from 15 Austrian sites.¹⁵ Data will be extracted for patients who meet the eligibility criteria outlined in [Section 9.2.1](#) and [9.2.2](#), resulting in an estimated 30 patients. The data to be abstracted or extracted will include but is not limited to baseline demographics and clinical characteristics, treatment patterns and effectiveness outcomes. Where required, treatment patterns and effectiveness outcomes will be defined using numerical and statistical methods. Initial feasibility investigations showed the registry extract data in a similar way to an eCRF and extract data from EMRs at multiple sites across Austria.

It is estimated that around 230 patients will be included across Austria, Belgium, and Germany; this comprises of 1 site plus 1 registry in Austria, 3 sites in Belgium and 1 site in Germany. However, the final number will vary from this estimate and that is permissible.

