9.5. Study Size

This study is purely descriptive and there will be no limit on the sample size in terms of patients meeting the eligibility criteria in [Section 9.2.1](#) and [9.2.2](#). Estimated sample sizes are presented below by county in Table 1. Sample sizes will be maximized where feasible and appropriate and will likely vary from the below estimates.

Table 1. Sample Size Estimations per Data Source

	Site name	Number of patients treated with GO
Austria	Medical University of Vienna	50
	Austrian Myeloid Registry	30
Belgium	UZ Leuven	50
	Az Sint Jan Brugge	42
	UZ Brussels	18
Germany	University of Cologne	40

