- For the chart review, selection bias may arise. Site participation is influenced by willingness to take part, and may be based on workload, levels of consulting patients during the data collection period, or familiarity with the research nature of the study. It should also be noted that the sites eligible for inclusion in the study are those with whom Pfizer have existing relationships with, and those ultimately selected for inclusion may be those deemed most suitable based on the feasibility assessment stage (ie, those sites with higher numbers of patients or who are most suited to executed non-interventional data collection studies) may be chosen over those considered to be less suitable. These factors introduce a bias whereby patients from non-participating sites are not represented in the results. Nonetheless, this method of site selection is the most practical approach for a non-interventional study such as this, whereby resources and timelines, to an extent, dictate the sites that can be considered eligible for inclusion.
- Further to the previous point, in the event that informed consent is required for patient participation, the patient sample may potentially be biased towards less severe patients who are capable and willing to provide consent to participate. To mitigate both of these selection biases, patient demographic and clinical characteristic data will be captured to allow for comparisons with published datasets to understand the generalizability of results. Additionally, should informed consent be required in Austria and/or Belgium and/or Germany, a legally acceptable representative would be permitted to provide informed consent on behalf of the patient should they be unable to consent, reducing the bias associated with the need to obtain patient consent. Based on initial information, informed consent is unlikely to be necessary to process pseudoanonymised data in Austria and Belgium, and is not required in Germany to process completely anonymised data. In order to avoid this limitation, efforts will be made to ensure a waiver for informed consent is provided by local IRBs.

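### Signed consent is mandatory in Belgium (110 of 230 planned patients), but Section 9.9 still treats it as unlikely and no section says how patients who died before consent are included, leaving OS at risk of upward bias

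*Protocol*

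**What the plan says.** Section 10.2 (Patient Consent) settles the matter for Belgium: "Following IRB review in Belgium, an informed consent document must be signed by the patient". The sentence goes on to accept a legal representative's signature instead, and Section 10.3 and inclusion criterion 6 repeat that route. Section 10.2 identifies the approved form as version 3.0 of 07 June 2023. Section 9.2 closes the indexing period on 31 May 2023.

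Section 9.9 (Limitations) reads differently: "informed consent is unlikely to be necessary to process pseudoanonymised data in Austria and Belgium". It says waivers will be pursued. It describes consent bias, if consent should be needed, as a shift towards less severe patients who are able and willing to sign. Its remedies are a representative for patients who cannot consent, and comparison of baseline data with published datasets.

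On deaths, Section 9.2 says: "Patients who die within the 3-month follow-up period would be considered eligible for inclusion in order to evaluate EFS, RFS and OS outcomes". Inclusion criterion 5 agrees.

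On size, Section 9.4 says: "It is estimated that around 230 patients will be included across Austria, Belgium, and Germany". The Belgian rows of Table 1 (Section 9.5) are UZ Leuven with 50, "Az Sint Jan Brugge 42" and "UZ Brussels 18".

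**The concern.** Sections 9.9 and 10.2 are both current text and cannot both be right for Belgium. The bias assessment in Section 9.9 is therefore out of date for nearly half of the sample.

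The mechanism that matters is survival to the consent date, and neither section names it. OS, EFS and RFS are all timed from the start of induction or first-line treatment (Section 9.3.2.2), whereas consent on the approved form always follows the indexing period. A living Belgian patient can sign. A deceased one enters only if a representative is found, is permitted to sign for someone who has died, and does so. The patients whom Section 9.2 deliberately keeps eligible are thus the hardest to include in Belgium.

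All sources are to be combined into one dataset (Section 9.3), so Belgian deaths that go missing would raise the pooled curves for a reason unrelated to treatment. Comparing baseline characteristics with published data need not reveal selection on later survival, and no analysis can recover patients who were never abstracted.

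**Working it through.** **1. Sample size and the Belgian share (Table 1).** 50 + 30 + 50 + 42 + 18 + 40 = 230, which reproduces the stated total. Belgium: 50 + 42 + 18 = 110, and 110/230 = 47.8%.

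**2. Time from index to consent.** Index dates run from 01 April 2018 to 31 May 2023. The Abstract gives data collection as 01 November 2023 to 30 April 2024. (Section 6 prints a 2024 start, which falls after its own end date, so the Abstract's date is used.) The protocol gives no dates for seeking consent; the two ends of data collection are taken as bounds.
- Consent on 01 November 2023: gap 5 to 67 months, mean 36; with uniform index dates, 89% exceed 12 months.
- Consent on 30 April 2024: gap 11 to 73 months, mean 42; 98% exceed 12 months.

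**3. Share dead before consent (illustration).** Median OS is assumed to be 27.5 months, the GO-arm figure of the phase 3 trial quoted in Section 7. With exponential survival, λ = ln 2/27.5 = 0.0252 per month. For gaps uniform between a and b, the share alive is (e^(−λa) − e^(−λb)) / (λ(b − a)).
- 01 November 2023 (a = 5.06, b = 67.02): (0.880 − 0.185)/1.562 = 0.445 alive, 55.5% dead.
- 30 April 2024 (a = 11.01, b = 72.97): (0.758 − 0.159)/1.562 = 0.383 alive, 61.7% dead.

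If a fraction c = 30% or 40% are long-term survivors and the median is unchanged, λ = −ln((0.5 − c)/(1 − c))/27.5 for the rest. The share dead is then 51.5% or 55.9% (c = 30%) and 49.5% or 52.9% (c = 40%) for the two dates. The overall range is about 50% to 62%, or 54 to 68 of 110 patients.

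**4. Effect on the pooled Kaplan-Meier estimate.** This was simulated with 1,000,000 patients per scenario. Let q be the share of deceased Belgian patients who still enter. All survivors are assumed to consent and all other sources to be complete. Paired values are for consent on 01 November 2023 / 30 April 2024.

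| Survival model | True 24-month OS | Pooled, q = 0 | Pooled, q = 0.5 | Pooled, q = 1 |
|---|---|---|---|---|
| Exponential | 54.6% | 66.6% / 65.9% | 59.6% / 59.2% | 54.6% |
| 30% long-term survivors | 53.4% | 67.0% / 66.5% | 59.2% / 58.9% | 53.4% |
| 40% long-term survivors | 52.5% | 67.0% / 66.7% | 58.7% / 58.6% | 52.5% |

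The rise at q = 0 runs from 65.9 − 54.6 = 11.3 to 67.0 − 52.5 = 14.5 points. At q = 0.5 it runs from 59.2 − 54.6 = 4.6 to 58.7 − 52.5 = 6.2 points. At q = 1 it is zero.

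The pooled median at q = 0 is 41 to 42 months (exponential) or not reached (long-term survivors); at q = 0.5 it is 32 to 48 months. Expected N at q = 0 is 162 to 176; for example, 230 − 110 × 0.617 = 162.

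**5. Scale for comparison.** The 95% half-width at a proportion of 50% is 1.96 × √(0.25/230) = 6.5 points for 230 patients, and 1.96 × √(0.25/120) = 8.9 points for the 120 outside Belgium.

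**The case against.** A reader might infer from Section 10.2 that only survivors can enter in Belgium, so that 110 of 230 patients are selected on being alive and the pooled survival results are certain to be inflated. The documents do not support that. The representative route is stated in Sections 10.2 and 10.3 and in criterion 6. How the approved form and the ethics committee treat deceased patients is not shown, and nothing says that a waiver for them was refused.

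Other points also stand:
- Section 9.9 does raise consent bias and representative consent. It is outdated and too narrow, not silent.
- RFS as written runs to relapse only, so missing deaths affect it indirectly, in so far as relapsed patients die more often. EFS also counts relapse and failure to reach remission, so the time before consent is free of deaths but not of EFS events.
- The consent gap is not years for everyone; it can be 5 months for the last patients indexed.
- The 27.5-month median comes from patients aged 50-70. This study takes adults from 18 with favourable or intermediate risk, so the share dead may be overstated.
- With half of the deceased included, the shift is no larger than the sampling half-width of 6.5 points. With three quarters included, an exponential model with consent on 01 February 2024 gives 56.8% against 54.7%, only 2.1 points.
- Survival is a secondary objective of a descriptive study.

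These points limit the size and certainty of the bias. They do not remove the contradiction or supply the missing rule for deceased patients. Nor can the matter simply be left to the SAP: eligibility, consent and limitations are protocol content, and sites must delete linkage information at close-out (Section 9.6).

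**Conclusion.** The point holds as an uncontrolled risk, not as a demonstrated loss. Sections 9.9 and 10.2 contradict each other for 48% of the planned sample, and the protocol does not say how Belgian patients who died before consent are included. If some of them are not, OS is biased upward, EFS partly, and RFS indirectly.

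The size depends on the share of deceased patients who enter, which the documents do not give: about 11-15 points on pooled 24-month OS for none, 5-6 for half, 0 for all. These figures rest on an assumed 27.5-month median, uniform index dates, consent sought during the planned data collection, full consent among survivors, and complete capture elsewhere. They illustrate scale and are not study estimates; in particular, the zero-inclusion figures should not be read as the expected result.

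**What to change.** 1. Reconcile Section 9.9 with Section 10.2. State that consent is required in Belgium, and name survival to the consent date as a selection mechanism affecting 110 of 230 planned patients.
2. State how deceased Belgian patients enter: by representative consent, or by an ethics committee waiver for deceased patients.
3. Before linkage is deleted, have each Belgian site report aggregate counts of eligible GO-treated patients by vital status and consent outcome. The share of deaths captured then becomes a known quantity.
4. Prespecify OS, EFS, RFS and time to next treatment with and without the sources where signed consent was required. Keep Belgium in the treatment-pattern description. Define those sources by what each ethics committee actually required: criterion 6 also covers the Austrian and German sites, and the statement in Section 9.9 that Austria is unlikely to need consent is not firm.

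Two stronger remedies are not recommended as the default. Removing Belgium from the main survival estimates in advance gives up 48% of the sample whatever share of deaths is captured. Delayed entry at the consent date leaves little time at risk (at most about 6 months for patients who consent between 01 November 2023 and 30 April 2024) and cannot handle patients entered after death.

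The cost is protocol wording, possibly one ethics request, and a small amount of site work. The estimate without Belgium is less precise: about 120 patients, with a half-width of about 9 instead of 6.5 points at 50%.

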10.3. Patient Withdrawal

In Belgium, patients (or a patient's legal representative) will be asked to sign the informed consent document through their physician (see [Section 10.2](#)). After signing the informed consent document, a patient is not required to do anything further in the study. However, should a patient wish to withdraw from the study, the informed consent document details that a participant is free to stop participation at any time, with no consequence to their medical care.

10.4. Institutional Review Board (IRB)/Independent Ethics Committee (IEC)

There must be prospective approval of the study protocol, protocol amendments, and other relevant documents (eg, informed consent forms if applicable) from the relevant IRBs/IECs. All correspondence with the IRB/IEC must be retained. Copies of IRB/IEC approvals must be forwarded to Pfizer.

10.5. Ethical Conduct of the Study

The study will be conducted in accordance with legal and regulatory requirements, as well as with scientific purpose, value and rigor and follow generally accepted research practices described in:

- Guidelines for Good Pharmacoepidemiology Practices (GPP). Public Policy Committee, International Society of Pharmacoepidemiology. Pharmacoepidemiology and Drug Safety 2016; 25:2-10.
- Good Practices for Outcomes Research issued by the International Society for Pharmacoconomics and Outcomes Research (ISPOR)
- Good practices for real-world data studies of treatment and/or comparative effectiveness: Recommendations from the joint ISPOR-ISPE Special Task Force on real-world evidence in health care decision making
- International Ethical Guidelines for Epidemiological Studies issued by the Council for International Organizations of Medical Sciences (CIOMS)

- European Medicines Agency (EMA) European Network of Centres for Pharmacoepidemiology and Pharmacovigilance (ENCePP) Guide on Methodological Standards in Pharmacoepidemiology
- The ENCePP Code of Conduct for scientific independence and transparency in the conduct of pharmacoepidemiological and pharmacovigilance studies
- Food and Drug Administration (FDA) Guidance for Industry: Good Pharmacovigilance Practices and Pharmacoepidemiologic Assessment
- FDA Guidance for Industry and FDA Staff: Best Practices for Conducting and Reporting Pharmacoepidemiologic Safety Studies Using Electronic Healthcare Data
- FDA Guidance for Industry: Patient-Reported Outcome Measures: Use in Medical Product Development to Support Labeling Claims
<http://www.fda.gov/downloads/Drugs/Guidances/UCM193282.pdf>.

11. MANAGEMENT AND REPORTING OF ADVERSE EVENTS/ADVERSE REACTIONS

Structured Data Analysis:

- This study involves data that exist as structured data by the time of study start. In these data sources, individual patient data are not retrieved or validated, and it is not possible to link (ie, identify a potential association between) a particular product and medical event for any individual. Thus, the minimum criteria for reporting an adverse event (AE) (ie, identifiable patient, identifiable reporter, a suspect product, and event) cannot be met.

Human Review of Unstructured Data:

This study protocol requires human review of patient-level unstructured data; unstructured data refer to verbatim medical data, including text-based descriptions and visual depictions of medical information, such as medical records, images of physician notes, neurological scans, X-rays, or narrative fields in a database. The reviewer is obligated to report AEs with explicit attribution to any Pfizer drug that appear in the reviewed information (defined per the patient population and study period specified in the protocol). Explicit attribution is not inferred by a temporal relationship between drug administration and an AE but must be based on a definite statement of causality by a healthcare provider linking drug administration to the AE. The requirements for reporting safety events on the non-interventional study (NIS) adverse event monitoring (AEM) Report Form to Pfizer Safety are as follows:

- All serious and non-serious AEs with explicit attribution to **any Pfizer drug** that appear in the reviewed information must be recorded on the NIS AEM Report Form included in [Annex 3 \(Appendix 2\)](#), and reported within 24 hours of awareness to Pfizer Safety.
- Scenarios involving drug exposure, including exposure during pregnancy, exposure during breast feeding, medication error, overdose, misuse, extravasation, lack of efficacy, and occupational exposure associated with the use of a Pfizer product must be reported, within 24 hours of awareness, to Pfizer Safety using the NIS AEM Report Form.
- For exposure during pregnancy in studies of pregnant women, data on the exposure to GO during pregnancy, are not reportable unless associated with serious or non-serious adverse events.
- For these AEs with an explicit attribution or scenarios involving exposure to a Pfizer product, the safety information identified in the unstructured data reviewed is captured in the Event Narrative section of the report form, and constitutes all clinical information known regarding these AEs. No follow-up on related AEs will be conducted.

All the demographic fields on the NIS AEM Report Form may not necessarily be completed, as the form designates, since not all elements will be available due to privacy concerns with the use of secondary data sources. While not all demographic fields will be completed, at the very least, at least one patient identifier (eg, gender, age as captured in the narrative field of the form) will be reported on the NIS AEM Report Form, thus allowing the report to be considered a valid one in accordance with pharmacovigilance legislation. All identifiers will be limited to generalities, such as the statement “A 35-year-old female...” or “An elderly male...” Other identifiers will have been removed. Additionally, the onset/start dates and stop dates for “Illness,” “Study Drug”, and “Drug Name” may be documented in month/year (mmm/yyyy) format rather than identifying the actual date of occurrence within the month/year of occurrence in the day/month/year (DD/MMM/YYYY) format.”

All research staff members must complete the following Pfizer training requirements:

- *“Your Reporting Responsibilities (YRR) with Supplemental Topics.”*

These trainings must be completed by research staff members prior to the start of data collection. All trainings include a “Confirmation of Training Statement” (for signature by the trainee) as a record of completion of the training, which must be kept in a retrievable format. Copies of all signed training certificates must be provided to Pfizer. Re-training must be completed on an annual basis using the most current Your Reporting Responsibilities training materials.

- Re-training must be completed on an annual basis using the most current Your Reporting Responsibilities (YRR) with Supplemental Topics training materials. Where Pfizer issues an updated safety training program, including during the course of a calendar year, vendor shall ensure all vendor personnel complete the updated safety training within sixty (60) calendar days of issuance by Pfizer.

